10. INVESTIGATIONAL MEDICINAL PRODUCT

10.1. Investigational Medicinal Product Supply and Control

FDC, EZE, and PBO tablets and overencapsulated tablets will be supplied to the sites by Esperion Therapeutics. The IMP will be distributed and released in accordance with regional and local requirements during the conduct of the study. Study medication will be stored under lock and key, with access limited to those authorized by the investigator, and will be managed according to US Food and Drug Administration (FDA) regulations concerning the storage and administration of investigational drugs.

Additional information regarding packaging, labeling, storage, and distribution is provided in the pharmacy manual.

10.2. Administration of Investigational Medicinal Product

The dose of IMP will be administered to the subjects at the study site at each of the study visits. The first dose of single-blind PBO will be taken during Visit S2. Subsequent doses will be self-administered once daily by the subject at approximately the same time each day in the morning through Study Day -1 (the day prior to Visit T1). Double-blind IMP will be taken at Visit T1/Day 1 between 6 AM and 10 AM. The actual time of IMP administration during study visits will be recorded and will determine the target time of IMP administration for the subjects during the treatment period. Subjects will self-administer the IMP on all other days, once daily in the morning with or without food. The last dose of IMP will be taken on the morning of the day prior to Visit T3/EOS).

Subjects will be instructed on the importance of maintaining 24-hour intervals between doses. If the daily dose of IMP is not taken at the usual time due to unforeseen circumstances, the subject may take the dose as soon as possible after the target time but no later than noon. If the daily dose is not taken by noon, the subject will be instructed to skip the dose on that day and to resume dosing on schedule the next day.

10.3. Investigational Medicinal Product Accountability, Handling and Disposal

The Principal Investigator must maintain accurate records of the receipt of all study medication shipped by the sponsor/sponsor representative and the disposition of that study medication. The Principal Investigator will ensure that all IMP is stored in a secured area, under recommended storage conditions [REDACTED]

[REDACTED] in accordance with applicable regulatory requirements for investigational drugs. Access to IMP will be limited to those clinical site personnel authorized by the Investigator.

Upon completion or termination of the study, all used and unused IMP (FDC, EZE, and PBO) will be returned to the sponsor (or designee) for destruction or disposed of by the study site, per

sponsor written instruction. All IMP returns must be accompanied by the appropriate documentation.

Investigational medicinal product records or logs must comply with applicable regulations, local law, and guidelines, and should include:

- amount received/placed in storage area;
- amount currently in storage area;
- label identification or batch number;
- dates and initials of person responsible for product inventory (including entry/movement/disposition);
- date and amount dispensed to each subject, including unique subject identifier;
- data returned by subject, assessment of compliance, and relevant documentation of discrepancies;
- nonstudy disposition (eg, lost, broken, wasted); and
- amount returned to sponsor/sponsor designee.

The sponsor will provide forms to facilitate inventory control if the staff at the investigational site does not have an established quality system that meets the needs of this requirement.

11. STUDY PROCEDURES AND SCHEDULE OF ASSESSMENTS

11.1. Informed Consent

The investigator is responsible for providing each subject with adequate explanations of the nature and risks of the study before any study procedures or assessments occur. The subject must be able to understand the ICF and to converse with the investigator in the language in which the ICF is written. No study-related procedures will be performed until the subject has been completely informed of the study risks and benefits, has freely consented to take part in the study, and has signed and dated an ICF that has been approved by a licensed IRB.

11.2. Subject Identification Numbers

A unique subject identification number (subject ID) will be assigned to identify each subject throughout the study and will be entered on all documentation. If a subject is not eligible to receive treatment or discontinues from the study, that subject's identification number cannot be assigned to another subject. Subject identification numbers will be assigned sequentially.

11.3. Rescreening

Subjects who are screening failures due to stability requirements for a condition or concurrent medication or other reason may be considered for rescreening after consultation with the Sponsor (or designee). If rescreened, these subjects must also be re-consented and screening procedures must be repeated. If a subject is a screen failure, or if a subject discontinues from the study, their subject ID number will not be assigned to another subject. Rescreened subjects will be assigned a new subject ID number.

11.4. Procedures and Schedule of Assessments

The study is comprised of two distinct periods: the Screening and Run-in Period and the Treatment Period. The schedule of study events is provided in [Appendix 1](#). However, a subject can be seen at any time for reasons of safety.

All relevant data will be captured on electronic case report forms (eCRFs) according to the eCRF completion guidelines.

11.5. General Visit Guidelines

Subjects will arrive fasted and having not taken study medication prior to the visit. The following assessments will be conducted while fasted and prior to taking study medication (unless otherwise specified):

- Review of medical history, prior and concomitant medications;
- Assess AEs and SAEs;
- PE;
- Vital signs;

- blood sampling for basic fasting lipid assessments (LDL-C, non-HDL-C, TC, TG, HDL-C);
- blood sampling for special lipids and other biomarkers (apoB, hs-CRP, glucose, [REDACTED] HbA_{1C});
- blood sampling for clinical safety laboratories.

11.6. Screening Period

11.6.1. Screening Period Visit 1 (Visit S1/Day -42 ± 7)

Subjects will be screened for study eligibility at Visit S1 (Day -42 ± 7). The following evaluations will be performed at this visit:

- Written informed consent will be obtained before any study-related procedures are conducted.
- Demographic data will be recorded.
- Recent clinically relevant medical history will be recorded.
- Prior, concomitant, and prohibited medications will be reviewed and recorded.
- Weight (in kilograms) and height (in centimeters) will be measured, and BMI will be calculated.
- PE
- Vital signs (systolic blood pressure, diastolic blood pressure, and pulse rate) will be recorded.
- Blood and urine specimens will be obtained for the following:
 - serum pregnancy test (for surgically sterile women and women of childbearing potential) or FSH test (women <55 years old and ≥1 year without menses);
 - basic fasting lipid panel;
 - special lipids and other biomarkers (HbA_{1C} only);
 - coagulation panel;
 - serum TSH;
 - clinical safety laboratories (hematology, clinical chemistry, and urinalysis);
 - urine drug screen.
- eGFR will be calculated (by central laboratory) using the MDRD formula.
- Conduct diet and exercise counseling.
- Contact IWRS to register subject.

Subjects with a history of T2D of at least 6 months with at least 3 months on stable diabetes medication, who have an HbA_{1C} between 7%-10%, an LDL-C level >70 mg/dL, and meet the other protocol inclusion/exclusion criteria based on initial screening will be contacted by phone to schedule the second screening visit (Visit S2) to occur approximately 7 days after Visit S1.

Subjects who fail to meet any entry criterion that can be assessed at Visit S1 are considered to be screen failures and are not required to return for additional visits (although a subject can be seen at any time for safety reasons).

Under rare circumstances, subjects who are considered to be screen failures due to not meeting stability requirements for a condition or concurrent medication that is considered to warrant rescreening after consultation with the Sponsor (or designee) may be rescreened. These subjects must be re-consented, re-registered in the IWRS, and will have a new subject ID assigned.

11.6.2. Screening Period Visit 2 (Visit S2/Day -35 ± 3)

Subjects will undergo the following assessments and procedures at Visit S2:

- Review of all inclusion/exclusion criteria that can be assessed at this time;
- Concomitant and prohibited medication review (ongoing);
- Adverse events will be assessed (starting from signing of the informed consent);
- Electrocardiogram (ECG);
- Vital signs;
- Serology (including HBsAg, hepatitis C antibody);
- Conduct diet and exercise counseling;
- Instruct subject to stop taking all LMT and other prohibited medications ([Section 9.3.1](#));
- Dispense single-blind PBO with instructions;
- Schedule next visit.

11.6.3. Screening Period Visit 3 (Visit S3/Day -7 ± 3)

Subjects will undergo the following assessments and procedures at Visit S3:

- Review of all inclusion/exclusion criteria;
- Concomitant and prohibited medication review (ongoing);
- Adverse events will be assessed;
- Weight (in kilograms);
- Vital signs;
- Basic fasting lipids;
- Clinical safety laboratories;

- Conduct diet and exercise counseling;
- Assessment and recording of drug compliance with single-blind PBO;
- Schedule next visit.

11.7. Treatment Period

Enrollment criteria will be reviewed including select laboratory values from Visit S3. Subjects who have an LDL-C level between 100 to 220 mg/dL at Visit S3 and who meet all other inclusion/exclusion criteria will be scheduled for their first treatment visit (Visit T1/Day 1), and instructed to fast for a minimum of 10 hours (nothing but water) on the evening before reporting for Visit T1/Day 1.

11.7.1. Treatment Period Visit 1 (Visit T1/Day 1)

Subjects will be scheduled for their first treatment visit approximately 7 days after completion of Visit S3/Day -7. Subjects will arrive at the study site after a minimum 10-hour fast, will be administered their first dose of IMP at this visit.

Procedures and evaluations will be performed in the following order during this visit:

- Enrollment criteria will be reviewed.
- Concomitant and prohibited medications will be reviewed and recorded as needed.
- Adverse events will be assessed.
- Weight (in kilograms) will be recorded.
- Vital signs (systolic blood pressure, diastolic blood pressure, and pulse rate) will be recorded.
- Blood and urine specimens will be obtained for the following:
 - urine pregnancy test (for women of childbearing potential);
 - basic fasting lipid panel;
 - special lipids and other biomarkers;
 - clinical safety laboratories (hematology, clinical chemistry, and urinalysis);
 - reserve sample for potential exploratory biomarkers; and
 - urine drug screen.
- Subject will be given 1 serving of Ensure Original Vanilla[®] breakfast drink (Abbott Laboratories: 220 calories, 32 g of total carbohydrate) at approximately 9:00 AM and will record the time of the meal.
- Blood sample for PPG (glucose only) will be collected 2 hours \pm 5 minutes after the subject consumes the Ensure breakfast drink for the 2-hour postprandial glucose assessment.

- Subjects will be randomized to a treatment (once daily dosing of FDC, EZE, or PBO IMP).
- Double-blind IMP will be dispensed and subject will be provided with dosing and storage instructions.
- Subjects will take their first dose of IMP, with approximately 8 ounces of water, following collection of the 2-hour PPG blood glucose sample collection.
- Conduct diet and exercise counseling.

11.7.2. Treatment Period Visit 2 (Visit T2/Day 28 ± 3)

Subjects will be scheduled for their second Treatment Period Visit approximately 27 days after completion of Visit T1/Day 1. Subjects will arrive at the study site after a minimum 10-hour fast, having not yet taken the daily dose of IMP.

Procedures and evaluations will be performed in the following order during this visit:

- Return of IMP; assessment and recording of IMP dosing adherence.
- Concomitant and prohibited medications will be reviewed and recorded as needed.
- Adverse events will be assessed.
- Vital signs (systolic blood pressure, diastolic blood pressure, and pulse rate) will be recorded.
- Blood and urine specimens will be obtained for the following:
 - basic fasting lipid panel;
 - special lipids and other biomarkers;
 - clinical safety laboratories (hematology, clinical chemistry, and urinalysis).
- Subject will be given 1 serving of Ensure Original Vanilla breakfast drink (Abbott Laboratories: 220 calories, 32 g of total carbohydrate) at approximately 9:00 AM and will record the time of the meal.
- Blood sample for PPG (glucose only) will be collected 2 hours ± 5 minutes after the subject consumes the Ensure breakfast drink for the 2-hour postprandial glucose assessment.
- Double-blind IMP dispensed.
- Subjects will take their daily dose of IMP, with approximately 8 ounces of water, following collection of the 2-hour PPG blood glucose sample collection.
- Conduct diet and exercise counseling.

11.7.3. Treatment Visit 3 (Visit T3/EOS/Day 85 ± 3)

Subjects will be scheduled for their final Treatment Period Visit approximately 84 days after completion of Visit S1/Day 1. Subjects will arrive at the study site after a minimum 10-hour fast, having taken the final dose of IMP approximately 24-hours earlier on the previous day.

Procedures and evaluations will be performed in the following order during this visit:

- Return of IMP; assessment and recording of IMP dosing adherence.
- Concomitant and prohibited medications will be reviewed and recorded as needed.
- Adverse events will be assessed.
- Weight (in kilograms) will be recorded.
- PE.
- Vital signs (systolic blood pressure, diastolic blood pressure, and pulse rate) will be recorded.
- Blood and urine specimens will be obtained for the following:
 - urine pregnancy test (for women of childbearing potential);
 - basic fasting lipid panel;
 - special lipids and other biomarkers;
 - clinical safety laboratories (hematology, clinical chemistry, and urinalysis)
 - reserve sample for potential exploratory biomarkers.
- Subject will be given 1 serving of Ensure Original Vanilla breakfast drink (Abbott Laboratories: 220 calories, 32 g of total carbohydrate) at approximately 9:00 AM and will record the time of the meal.
- Sample for PPG blood glucose will be collected 2 hours ± 5 minutes after the subject consumes the Ensure breakfast drink for the 2-hour postprandial glucose assessment.
- Subjects will be notified they may begin taking any LMT medications washed out during study participation at the conclusion of the visit.
- Complete study status in IWRS (ie, early withdrawal or completed study).

11.8. Subject Withdrawal Criteria

11.8.1. Early Withdrawal from Study

Subjects must remain in the study through Week 12 (Visit T3/Day 85 ± 3) to be considered as having completed the study. Subjects who prematurely withdraw from the study will be asked to continue to be followed for safety, as outlined in [Appendix 1](#).

Participation in the study is voluntary. Subjects may refuse or withdraw from participation in this study at any time and for any reason, specified or unspecified, and without penalty or loss of benefits to which the subject is otherwise entitled.

The investigator has the right and duty to interrupt the treatment of any subject whose health or well-being may be threatened by continued participation in this study. Such subjects should be withdrawn from the study and should not be continued under a modified regimen.

Subjects who are withdrawn from the study may not re-enter the study. The reasons for study withdrawal may include:

- Adverse event;
- Subject withdrawal of consent;
- Failure to comply with the protocol;
- Refusal to take IMP as indicated by the protocol;
- Illness, condition, or procedural complication that affects the subject's ability to participate in the study or that requires prohibited medication;
- Sponsor or investigator terminates the study;
- In the investigator's judgment, it is in the subject's best interest to discontinue participation in the study;
- Other (specify).

If a subject is lost to follow-up, study site personnel must make reasonable efforts to contact the subject to determine the reason for discontinuation/withdrawal. The measures that are taken to follow-up must be documented.

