13.6.3. General Monitoring and Management of Abnormal Clinical Laboratory Values

The investigator will review the results of all laboratory tests as they become available and will sign and date the report to document their review. The investigator will ascertain if any laboratory value is abnormal or represents a clinically significant change from baseline for the individual subject, with baseline defined as the last value or observation before the first dose of IMP. The investigator may repeat the laboratory test or request additional tests to verify the results of the original laboratory test.

If a laboratory value is determined to be an abnormal and clinically significant change from baseline for the subject, the investigator will determine if it qualifies as an AE (as described below), and if yes, an appropriate eCRF will be completed. All clinically significant laboratory abnormalities that occur during the study that were not present at baseline should be followed and evaluated with additional tests, if necessary, until diagnosis of the underlying cause or resolution. Specific monitoring and management guidelines for laboratories of special interest are outlined in the sections below.

An abnormal laboratory value that is not already associated with an AE is to be recorded as an AE only if any one of the following criteria is met:

- an action is taken with the imp because of the abnormality;
- intervention for management of the abnormality is required; or
- the abnormality be deemed clinically significant by the investigator.

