13.6.3.1. Monitoring and Management of Elevated Liver Function Tests

If a subject has a new value $>3 \times \text{ULN}$ for serum ALT and/or AST at any time after randomization, the subject will undergo a repeat confirmatory liver function test (LFT) assessment as soon as is reasonably possible but preferably within 3 to 7 days after the laboratory result is available.

Repeat LFT assessment will include the following: (1) measurement of serum ALT, AST, alkaline phosphatase, TB, direct bilirubin, and CK; prothrombin time (PT)/international normalized ratio (INR); eosinophil count; and antihepatitis A virus (total), HBsAg (confirmation of screening measurement), HCV (confirmation of screening measurement), and anticytomegalovirus/immunoglobulin M; (2) history of concomitant medication use; (3) history of exposure to environmental chemical agents, including ethanol; and (4) questioning for related symptoms. Additionally, further testing, such as liver ultrasound or magnetic resonance imaging (MRI) scanning, may be warranted to rule out additional pathology depending on clinical presentation and should be discussed with the sponsor personnel or the authorized medical monitor.

- If the repeat LFT assessment confirms that the value for serum ALT and/or AST is $>3 \times \text{ULN}$, consideration should be given to withdrawing the subject and administering no further doses of IMP. At the investigator's discretion, IMP may be interrupted and the subject may be rechallenged with the IMP after values for the LFTs have returned to baseline levels.
- If repeat LFT assessment confirms a value for serum ALT and/or AST $>5 \times \text{ULN}$, the subject will be withdrawn from IMP treatment but will be asked to continue to be followed for safety (as outlined in the protocol-specified visit schedule in [Appendix 1](#) or more frequently as determined by the investigator).
- If repeat LFT assessment confirms that the value for serum ALT and/or AST level is $>3 \times \text{ULN}$ and the subject has any of the following findings, the subject will be withdrawn from IMP treatment but will be asked to continue to be followed for safety (as outlined in the protocol-specified visit schedule in [Appendix 1](#) or more frequently as determined by the investigator):
 - TB value $>2 \times \text{ULN}$;
Note: In the case of subjects with Gilbert's disease, TB will be fractionated and the determination of $2 \times \text{ULN}$ will be based upon direct (conjugated) bilirubin.

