13.6.3.4. Monitoring and Management of Elevated Creatine Kinase Levels

If a subject has a value $>5 \times \text{ULN}$ for serum CK at any time after randomization, the subject will undergo a repeat confirmatory assessment as soon as is reasonably possible but preferably within 3 to 7 days after the laboratory result is available. This assessment will include questioning for related symptoms.

- If the repeat CK assessment confirms an unexplained (ie, not associated with recent trauma or physically strenuous activity) CK abnormality (value $>5 \times \text{ULN}$), the subject should, if asymptomatic, receive further assessment and investigation into the cause. The presence of renal injury should be assessed, and serum CK levels should be measured approximately weekly or more frequently, if clinically indicated, until resolution. If serum CK levels continue to rise, treatment with the IMP should be discontinued.
- If symptomatic, the following steps should be completed:
 - Hold dosing with the IMP;
 - Clarify the nature, duration, and intensity of muscle symptoms;
 - Review possible predisposing factors, such as unaccustomed exercise, heavy alcohol intake, viral illness (consider performing serology);
 - Evaluate for additional diagnoses or other conditions, which can cause myopathy, including muscle tenderness (by PE), weakness, rash, measurement of serum creatinine level, and dipstick urinalysis with microscopy, if indicated;
 - Obtain clinical chemistries to assess the possibility of lactic acidosis; and
 - Follow symptoms and serum CK levels until the abnormality has resolved.

If, based on the above evaluation, an alternative explanation is suspected, consider resuming IMP once the serum CK level returns to baseline levels. If no alternative explanation exists, consider withdrawing the subject from IMP treatment.

- If the repeat assessment confirms an unexplained (ie, not associated with recent trauma or physically strenuous activity) CK abnormality (serum CK value $>10 \times \text{ULN}$) even in the absence of symptoms, the subject should be withdrawn from the study and given no further doses of IMP. In all cases, signs/symptoms and laboratory evaluations, as outlined in the bulleted point above, should be evaluated.
- If the subject is withdrawn from IMP treatment, the subject should be asked to continue to be followed for safety (as outlined in the protocol-specified visit schedule in [Appendix 1](#)).

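### Protocol 11.8.1 and the CK >10×ULN rule word a health-related stop of study drug as leaving the study, so an early end-of-study draw may stand in for the Day 85 LDL-C

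*Protocol*

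**What the plan says.** Protocol 11.8.1 gives the investigator the duty to interrupt treatment for a subject "whose health or well-being may be threatened by continued participation in this study". It continues: "Such subjects should be withdrawn from the study and should not be continued under a modified regimen". It adds: "Subjects who are withdrawn from the study may not re-enter the study". For those who leave, it states: "Subjects who prematurely withdraw from the study will be asked to continue to be followed for safety", with a pointer to Appendix 1.

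Section 13.6.3.4 gives the same instruction for a confirmed, unexplained creatine kinase (CK) value above 10 times the upper limit of normal (ULN): withdraw from the study and give no more IMP.

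Elsewhere the plan separates the two events. Section 7.1, the synopsis and SAP 4.2 ask subjects who stop IMP to stay on the scheduled visits for both safety and efficacy. The liver, eGFR and hemoglobin rules in 13.6.3.1 to 13.6.3.3 withdraw the subject from IMP only. For liver tests, "IMP may be interrupted and the subject may be rechallenged with the IMP". For symptomatic CK elevations with another likely cause, the site may "consider resuming IMP once the serum CK level returns to baseline levels".

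**The concern.** The same clinical event can be handled in two ways. A site reading 7.1 stops the drug and brings the subject back at Week 12. A site reading 11.8.1 ends participation and does the end-of-study (EOS) visit at once. Neither document says which text prevails.

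At stake is the primary endpoint, percent change in LDL-C to Week 12. In the second case the lipid panel may be taken while drug effect persists, and no Day 85 value may follow. SAP 5.2.1.1 includes every randomized subject who took at least one dose and has no recent-dosing condition, so an off-drug Day 85 value would count in the analysis if it were collected. There is also a practical safety ambiguity: whether a subject on a liver-test or CK hold may be rechallenged.

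**Working it through.** The plan gives no figure on this point, so the check is mainly a comparison of texts.

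**Step 1. What each text does with a health-related stop**

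| Place | Stops IMP | Leaves study | Follow-up stated |
|---|---|---|---|
| 7.1, synopsis, SAP 4.2 | yes | no | safety and efficacy |
| 13.6.3.1 liver, 13.6.3.2 eGFR, 13.6.3.3 hemoglobin | yes | no | safety |
| 13.6.3.1 and 13.6.3.4 hold options | temporarily | no | restart possible |
| 13.6.3.4, CK >10×ULN | yes | yes | none in that bullet |
| 13.6.3.4, following bullet | yes | no | safety |
| 11.8.1 | yes | yes | safety, per Appendix 1 |

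The 11.8.1 and CK >10×ULN rows stand against the others, and the CK section is inconsistent within itself. Only 7.1, the synopsis and SAP 4.2 promise efficacy follow-up.

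**Step 2. From study withdrawal to the primary analysis**

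- Section 11.8.2 and Appendix 1 footnote a call for the T3/EOS procedures, including the lipid panel, at discontinuation.
- T3 is scheduled for Day 85 ± 3, that is Days 82 to 88. SAP 5.1 assigns any draw from Day 57 onward to Week 12, so an early EOS draw on Days 57 to 81 counts as an observed Week 12 value.
- A draw on Days 2 to 56 is assigned to Week 4. If it is the last postbaseline value, SAP 5.3.2 carries it to Week 12 (LOCF).
- The observed-case analysis in SAP 5.3.3 keeps the Day 57+ draw and omits the earlier one. It does not recover a Day 85 value that was never taken.

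**Step 3. Size, for illustration only**

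The documents do not say how many subjects would be affected or how far LDL-C rebounds. Assumptions: on-drug change of -40 points (FDC) or -20 (EZE), full drug effect at the early draw, no lipid-modifying therapy (LMT) restart, and a share r of the effect persisting at Day 85. The 78 per arm is from SAP 4.4.

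Shift in arm mean per replaced value = effect × (1 − r) / 78.

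- FDC: 40/78 = 0.51 points at r = 0; 20/78 = 0.26 at r = 0.5.
- EZE: 20/78 = 0.26 at r = 0; 10/78 = 0.13 at r = 0.5.
- FDC versus EZE, one subject in each arm: (40 − 20)/78 = 0.26 at r = 0; 0.13 at r = 0.5.

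As a fraction f of an active arm, with the whole effect D lost by Day 85, the estimate exceeds the Day 85 effect by f × D. For D of 20 to 40 points:

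- f = 2%: 0.4 to 0.8 points
- f = 5%: 1.0 to 2.0 points
- f = 10%: 2.0 to 4.0 points

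Using the Day 85 values instead would lower power for one comparison from 96.3% to 95.7%, 94.5% and 92.1% respectively (assumed standardized effect 0.6, two-sided 5%, 78 per arm).

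**The case against.** The strongest reply is that follow-up is already largely covered. Section 11.8.1 refers even study withdrawals to Appendix 1, which has no separate safety-only schedule and includes the lipid panel at T2 and T3. Section 11.8.2 urges that all visits be completed on time. This stands, and it is why the loss is only possible. It does not remove the instruction to leave the study, and 11.8.1 names safety alone.

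A second reply is that 11.8.1 concerns leaving the study, while 13.6.3 is the specific rule: "Specific monitoring and management guidelines for laboratories of special interest are outlined in the sections below". Restarting the same fixed dose is also not plainly a modified regimen. A sensible site could read it so, but the protocol does not say so, and the CK >10×ULN bullet sits inside 13.6.3 itself.

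Three stronger readings are tempting and not supported:

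- A reader might infer that a Day 85 value after an early EOS visit would reflect unrecorded LMT, since 11.7.3 releases subjects to restart it. But the T3 column of Appendix 1 and 11.7.3 both call for medication review at that visit, and SAP 5.2.8 counts medications started within 30 days of the last dose.
- A reader might infer that restarting LMT is itself a ground for exit, from "or that requires prohibited medication". That phrase qualifies an illness, condition or procedural complication in a list of possible reasons. Resuming LMT is not plainly one of these.
- A reader might charge this wording with the 28 days (85 − 57) by which a draw can be early and still count as Week 12, or with carry-forward of 29 to 83 days (85 − 56 to 85 − 2). Those intervals come from the SAP windows and LOCF, apply to any early leaver, and would remain after the fix. Likewise, exclusion from the completer set follows from stopping treatment.

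**Conclusion.** The conflict is real and lies in the text. Two places order study withdrawal for a health-related IMP stop, against the general design statement in both documents and against the IMP-only and hold-and-restart rules. Where a site follows 11.8.1, an early EOS lipid value can stand in for Day 85.

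The effect on the result is probably small. The 0.13 to 0.51 points per subject rests on assumed effects and rebound. It is smaller if drug effect has already faded at the early draw, and zero where Appendix 1 follow-up obtains the Day 85 value and the analysis uses it. The efficacy analysis set excludes three sites, so its arms may be below 78 and the per-subject shift larger; the documents do not say by how much. The documents do not support a claim that the primary conclusion is at risk. The reason to act is that a stated rule can discard a primary-endpoint value, and the remedy is already written in 7.1.

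**What to change.** Amend the protocol as follows:

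- In 11.8.1 and the CK >10×ULN bullet, replace withdrawal from the study with withdrawal from IMP treatment. In 11.8.1, cross-refer to 13.6.3 for hold and rechallenge.
- In 11.8.1 and 13.6.3, state that consenting subjects off IMP stay on the Appendix 1 schedule for safety and efficacy, including the T2 and T3 lipid panels.
- Keep the early EOS visit in 11.8.2 for subjects who truly leave the study. The SAP windows and LOCF continue to apply to them.

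The stopping and rechallenge thresholds stay with the sponsor's clinicians. The cost is amendment text and a note to sites, with no visits beyond Appendix 1 and no new data field. One small downside is that some subjects off IMP may restart LMT before Day 85, which would alter their LDL-C. The existing concomitant-medication record at T3 would capture this.
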